## 15.5 Physical Examination

Physical examination results will be summarized as normal, abnormal – not clinically significant, or abnormal – clinically significant using descriptive statistics at baseline and at each postbaseline time point.

Physical examination results will be presented in a listing.

## 15.6 Electrocardiogram

ECG parameters (ventricular rate, RR, PR, QRS, QT, QTcF and QTcB) will be summarized using descriptive statistics at baseline and at each post baseline time point. Changes from baseline will also be summarized. Interpretation results will present the number and percentage of normal, abnormal not clinically significant, and abnormal clinically significant results at each visit.

In addition, a categorical summary of abnormal corrected QT interval values will be presented. At each time point, the number of subjects with QTcF values of >450 ms, >480 ms, and >500 ms will be presented. At each postbaseline time point, the number of subjects with change from baseline values in QTcF of >30 ms and >60 ms will be presented.

Electrocardiogram results will be presented in a listing.

## 15.7 Columbia Suicide Severity Rating Scale (C-SSRS)

The C-SSRS is a questionnaire used to measure the presence and intensity of suicidal ideation and behavior. C-SSRS Screening/Baseline version used at Screening Visit and the since Last Visit version used at all other visits and will be administered prior to dosing. The C-SSRS includes “yes” or “no” responses for assessment of suicidal ideation and behavior as well as numeric ratings for severity of ideation, if present (from 1 to 5, with 5 being the most severe).

Suicidal Ideation items include:

Category 1 – Wish to be Dead

Category 2 – Non-specific Active Suicidal Thoughts

Category 3 – Active Suicidal Ideation with Any Methods (Not Plan) without Intent to Act

Category 4 – Active Suicidal Ideation with Some Intent to Act, without Specific Plan

Category 5 – Active Suicidal Ideation with Specific Plan and Intent

Suicidal Behavior items include:

- Category 6 – Preparatory Acts or Behavior
- Category 7 – Aborted Attempt
- Category 8 – Interrupted Attempt
- Category 9 – Actual Attempt (non-fatal)
- Category 10 – Completed Suicide

Self-injurious behavior without suicidal intent is also a C-SSRS outcome (although not suicide-related) and has a binary response (yes/no).

### Endpoints:

Composite endpoints based on the above categories are defined as follows:

- Suicidal **ideation**: A “yes” answer at any time during treatment to any one of the five suicidal ideation questions (Categories 1-5) on the C-SSRS.
- Suicidal **behavior**: A “yes” answer at any time during treatment to any one of the five suicidal behavior questions (Categories 6-10) on the C-SSRS.
- Suicidal **ideation or behavior**: A “yes” answer at any time during treatment to any one of the ten suicidal ideation and behavior questions (Categories 1-10) on the C-SSRS.

Tables will include results from the Suicidal Ideation and Suicidal Behavior sections of the C-SSRS. Frequencies and percentages of participants with a response of “Yes” at any post-Baseline point as well as by study visit on the Suicidal Ideation and Suicidal Behavior items will be summarized by treatment received. A listing will be produced to present all C-SSRS data for subjects with any post-baseline suicidal ideation or behavior.

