study treatment). In the CT1812 100 mg arm, two cases of post-dose neurological examination findings were assessed as clinically significant for coordination (bilateral ideomotor apraxia) and mental state (presence of delusions). There were 2 subjects (CT1812 100 mg and 300 mg treatment arms) with suicidal ideation as assessed by the C-SSRS.

A Phase 1 trial (COG0104) was a pilot study to evaluate the effect of CT1812 treatment on A β oligomer displacement into CSF in subjects with Mild to Moderate Alzheimer's Disease. Subjects were randomized to CT1812 560 mg/280 mg or placebo in a 1:1 ratio. A single dose was administered following insertion of an indwelling CSF lumbar catheter, and hourly CSF and plasma sampling was performed over a period of 24 hours to assess for oligomer displacement.

Overall, CT1812 was generally well tolerated in mild to moderate AD patients when delivered as a single dose of 560 mg.

There are several ongoing studies. COG0201 is a Phase 2 randomized, 6 month double-blind, placebo-controlled, parallel-group, study to evaluate the safety and efficacy of CT1812 in subjects with mild to moderate Alzheimer's disease with a target enrollment of 120 subjects. Subjects are randomized to one of three treatment arms (CT1812 at doses of 100 or 300 mg/d or placebo, n=40/group). To date 62 subjects have randomized. There have been several episodes of LFT elevation at various timepoints that have resolved following drug discontinuation or spontaneously. No SAEs have been considered drug-related.

COG0202 is a Phase 2 randomized, double-blind, placebo-controlled electroencephalography (EEG) study to evaluate the Effect of CT1812 Treatment on Synaptic Activity in Subjects with Mild to Moderate Alzheimer's Disease. This is a single-site, 16 subject, 29-day, 2-period crossover Phase 2 study of 1 dose level of CT1812 (300 mg) or placebo randomized in a 1:1 ratio. The purpose is to evaluate the efficacy of CT1812 in restoring synaptic function in subjects with mild to moderate Alzheimer's disease (AD) through quantitative EEG measurements, as reflected by relative theta power.

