5.2 Endpoints

5.2.1 Safety Endpoints

- The incidence and severity of adverse events.
- The change in usage of concomitant medications.
- Changes in vital signs.
- Changes in physical exam findings.
- Changes in electrocardiogram findings.
- Changes in clinical laboratory testing (serum chemistry, hematology, urinalysis).
- Changes in the Columbia Suicide Severity Rating Scale (C-SSRS).

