14.4.2 Safety Analyses

Adverse events (AEs) will be assessed by the investigator for severity and will be coded for summarization using Medical Dictionary for Regulatory Activities (MedDRA® Version 24 or higher). The occurrence of AEs will be summarized by treatment using MedDRA system organ classification, preferred terms, and severity. Separate summaries of AEs, serious AEs, AEs related to study drug, and AEs leading to study discontinuation will be summarized by Preferred Term and System Organ Class.

Concomitant medications will be coded using WHO Drug Dictionary (enhanced) March 2021 or higher and summarized.

Laboratory measures will be summarized by treatment group and time-point both as absolute values and as change from baseline, with descriptive statistics summarizing each group and time point. Similar presentation will be used for vital signs and for ECG interval measurements, and changes from pre-treatment baseline.

Results from Columbia Suicide Severity Rating Scale (C-SSRS) will be listed.

Results from physical exam findings will be listed.

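### SAP 15.7 plans no by-arm summary of change in the C-SSRS: any yes after dosing counts without reference to the pre-dose answers, and the composites and tables use different time windows

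*SAP*

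**What the plan says.** Protocol 5.2.1 lists among its safety endpoints "Changes in the Columbia Suicide Severity Rating Scale (C-SSRS"). The protocol's own analysis section (14.4.2) asks for less: "Results from Columbia Suicide Severity Rating Scale (C-SSRS) will be listed".

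SAP 15.7 goes further than 14.4.2. It defines three composites (ideation, behavior, either), each a yes to any of the relevant questions; for ideation this is a yes "at any time during treatment to any one of the five suicidal ideation questions". Its tables give the number and percentage answering yes "at any post-Baseline point as well as by study visit on the Suicidal Ideation and Suicidal Behavior items", by treatment received. It also plans a listing: "A listing will be produced to present all C-SSRS data for subjects with any post-baseline suicidal ideation or behavior".

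On timing of the instrument, the SAP states: "C-SSRS Screening/Baseline version used at Screening Visit and the since Last Visit version used at all other visits and will be administered prior to dosing". Protocol 9.2.1 and 9.2.2 place an administration at screening and another among the pre-dose assessments on Day 1. Protocol 9.2.12 places a further one at the Day 210 safety follow-up.

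SAP section 16, which records departures from the protocol, does not mention the C-SSRS.

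**The concern.** Safety and tolerability is the primary objective, and the program has a reason to look at this scale. Of an earlier trial in Alzheimer's disease with 23 dosed subjects, Protocol 3.3 reports: "There were 2 subjects (CT1812 100 mg and 300 mg treatment arms) with suicidal ideation as assessed by the C-SSRS". A reader of this trial's C-SSRS tables will want to know whether ideation after dosing is new or worse.

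The planned tables cannot answer that by arm. A subject who reported ideation before the first dose and reports it again afterwards, no more severely, is counted exactly like a subject whose ideation began on treatment. The SAP also describes a 1 to 5 severity for ideation but plans no comparison of it over time. With about 40 subjects per arm, a few carried-over cases could blur a real difference or suggest one that is not there.

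**Working it through.** **1. The named endpoint against the planned summaries.** The protocol endpoint is a change. SAP 15.7 contains any-yes composites, any-yes item tables and a listing. It contains no shift table, no change in ideation severity and no new or worsened category.

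**2. The same SAP's treatment of other safety data.**

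| Data | Use of the pre-dose state |
|---|---|
| Adverse events (15.1) | Pre-existing events count only if they worsened |
| Laboratory (15.3) | Change from baseline; shift tables for chemistry and hematology |
| Vital signs (15.4) | Change from baseline |
| ECG (15.6) | Change from baseline, with QTcF increase categories |
| C-SSRS (15.7) | None stated |

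**3. Can ideation be present at entry?** Protocol 8.3 has no criterion based on the C-SSRS or on suicidality. It excludes major psychiatric diagnoses, including current major depression, and limits the depression score, with an exception if the investigator does not consider the subject clinically depressed. Entry ideation is made less likely but not ruled out.

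**4. When does it count?** From Day 1 the version that asks about the time since the last visit is used. Entry ideation therefore reaches a post-baseline row only if it is reported again after dosing.

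**5. The two windows.** Protocol 12.2.1 defines the treatment period as first dose through last dose. The composites are limited to treatment; the tables run over all time after baseline, which takes in Day 210, about 28 days after dosing ends. A first yes at Day 210 is in the tables and outside the composites. This step needs no assumed rate.

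**6. Illustrative size.** The documents state no C-SSRS rate, so there is no figure to reproduce. Assumptions: q = proportion with ideation at entry, 2% to 10%; r = proportion of those who report it again after dosing, 25% to 100%; i = new onset in the rest, 2% to 5%. The arm size of 40 is from SAP section 5.

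Carried-over subjects per arm = 40 × q × r. New-onset subjects per arm = 40 × (1 − q) × i.

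- Lowest share carried over: 40 × 0.02 × 0.25 = 0.20 beside 40 × 0.98 × 0.05 = 1.96; 0.20 / 2.16 = 9%.
- Highest share: 40 × 0.10 × 1.00 = 4.00 beside 40 × 0.90 × 0.02 = 0.72; 4.00 / 4.72 = 85%.

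For chance imbalance, take two independent Binomial(40, qr) arms, counting carried-over cases only and assuming no drug effect. P(dose − placebo ≥ 2) is the sum over p of P(placebo = p) × P(dose ≥ p + 2). At qr = 0.02 the first three terms are 0.4457 × 0.1905 + 0.3638 × 0.0457 + 0.1448 × 0.0082 = 0.103.

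| q | r = 25% | r = 100% |
|---|---|---|
| 2% | qr 0.5%: 0.014 | qr 2%: 0.103 |
| 5% | qr 1.25%: 0.058 | qr 5%: 0.213 |
| 10% | qr 2.5%: 0.128 | qr 10%: 0.285 |

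**The case against.** The strongest defence is that the SAP already exceeds the protocol's analysis section, which asks only for a listing. Protocol 5.2.1 uses the same change wording for physical examination findings, and 14.4.2 plans only a listing there too. Protocol 11.1.12 speaks of assessing any occurrence of suicide-related thoughts and behavior, which an any-yes rule fits. This stands in part: the mismatch begins inside the protocol, between 5.2.1 and 14.4.2. But the SAP chose to define formal C-SSRS endpoints and left out the comparison that 5.2.1 names.

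A second defence is that the listing lets a reader check each case, and that with few cases this is enough. It does show pre-dose answers for subjects with a post-baseline event. As 15.7 specifies it, it leaves out subjects who had ideation before dosing and none afterwards. The general statement in SAP section 6 on listing individual data might be read more widely, but no listing gives counts by arm.

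Third, new or worsened ideation recorded as an adverse event would be tabulated on a treatment-emergent basis under SAP 15.1. True, but this depends on its being reported as an adverse event.

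Three stronger readings are tempting and are not supported:

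- A reader might infer that change is not measured. It is measured at screening, on Day 1 and later; what is missing is a planned summary.
- A reader might infer that ideation at entry is automatically scored as an on-drug event. The recall window of the later version means it counts only if reported again.
- A reader might infer that no table will show pre-dose answers. The by-visit table does not say which visits it covers, and screening and baseline are named visits in SAP section 7, so it may show them. Even then, visit-by-visit frequencies would not show within-subject change.

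**Conclusion.** The point holds as a gap in the planned summaries, of low severity. The change that Protocol 5.2.1 names has no summary by arm, although the pre-dose answers are collected and the same SAP uses baseline for adverse events, laboratory data, vital signs and ECG. The difference in windows is plain from the text.

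The size rests wholly on assumed rates. Carried-over subjects could number 0.2 to 4.0 per arm of 40, and the chance of an excess of at least 2 over placebo in a given dose arm runs from about 1% to 29%. An excess of 2 is an illustration only; the documents set no such decision rule, and C-SSRS is reported descriptively. It should not be read as bias against CT1812 or in its favor: randomization balances entry ideation in expectation, so the effect is inflated counts and chance imbalance. Chance imbalance would affect a new-or-worsened row too, but that row would not contain cases unchanged from before dosing.

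**What to change.** In SAP 15.7:

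- Add n (%) by arm with new or worsened ideation, and separately behavior: highest category after the first dose above the highest pre-dose category from screening and Day 1. State which recall period of the screening version is used, after checking the CRF, because the documents do not describe its recall periods.
- Add a shift table of highest pre-dose against highest on-treatment category, by arm.
- Keep the any-yes rows.
- State which visits the by-visit table covers, and whether screening and Day 1 are among them.
- Use one window for the composites and the tables, with Day 210 shown separately.

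The cost is SAP wording, a few table rows and one shift table. No new visit or assessment is needed; the one thing to confirm is that the CRF holds the screening answers in a form that separates the recall period chosen.

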### 15.8 Impact of COVID-19

Cases where SARS-CoV-2 coronavirus disease 2019 (COVID-19) had an impact on the study conduct of this trial will be presented in a listing.

## 16. CHANGES TO PROTOCOL-SPECIFIED ANALYSES

The following analyses in this SAP are different from Protocol version 3.0.

- The following analysis populations are included in this SAP but are not defined in the protocol: enrolled population, completers/compliers population, skin biopsy population. These populations have been added in order to facilitate summaries of data using applicable subject subsets of data.

## 18. APPENDICES

### APPENDIX A: PRESENTATION OF DATA AND PROGRAMMING SPECIFICATIONS

#### General

- Specialized text styles, such as bold, italics, borders, shading, and superscripted and subscripted text will not be used in tables, figures, and data listings (TFLs) unless they add significant value to the TLF.
- Only standard keyboard characters are to be used in tables and data listings.
- Special characters, such as nonprintable control characters and printer- or font-specific characters, will not be used in a TLF.
- Hexadecimal character representations are allowed (e.g.,  $\mu$ ,  $\alpha$ , and  $\beta$ ).
- All footnotes will be left justified and at the bottom of a page. Footnotes must be used sparingly and add value to the TLF.

#### Tables

- With the exception of PK data, means and medians will be presented to 1 decimal place more than the raw data. Standard deviations will be presented to 2 decimal places more than the raw data. Minimums and maximums will be reported with the same number of decimal places as the raw data.
- Percentages will be presented to the tenths place.
- For frequency counts of categorical variables, categories whose counts are zero will be displayed for the sake of completeness. For example, if none of the subjects discontinued due to “lost to follow-up,” this reason will be included in the table with a count of 0. Categories with zero counts will not have zero percentages displayed.
- Lower and upper CI values must be presented to 1 decimal place more than the raw/derived data (i.e., to the same number of decimal places as the mean).
- Percentiles (e.g., 25% and 75%) must be presented to 1 decimal place more than the raw/derived data.
- For all inferential analyses, *P* values will be rounded to 4 decimal places (or at the highest level of precision) with a leading zero (0.0001). *P* values less than 0.0001 will be presented as “<0.0001.”
- The last footnotes will be:
  - “Source: xxx”, where xxx indicates the source table number(s), if applicable (in case aggregated results, such as the mean or median, are plotted), source listing(s) (in case individual responses are plotted), and/or source dataset(s) (e.g., ADaM).
  - “PROGRAM SOURCE: ...\\xx.sas, DATA CUTOFF DATE: DD Mmm YYYY, RUN DATE: DD Mmm YYYY hh:mm”.

## Figures

- Legends will be used for all figures with more than 1 variable or item displayed.
- Figures will be in black and white but can be in color to add value to the clarity and readability of a figure. Lines must be wide enough to see the line after being copied.
- The last footnotes will be:
  - “Source: xxx”, where xxx indicates the source listing number(s) and/or source dataset(s) (e.g., ADaM).
  - “PROGRAM SOURCE: ...\\xx.sas, DATA CUTOFF DATE: DD Mmm YYYY, RUN DATE: DD Mmm YYYY hh:mm”.

## Listings

- If not otherwise specified, all data listings will be sorted by treatment, center, subject number, visit, and date/time, as appropriate.
- All date values will be presented in a SAS® statistical software, version 9.4 or higher (SAS Institute Inc) date format (eg, 29AUG2001).
- All observed time values will be presented using a 24-hour clock format (HH:MM:SS) (eg, 01:35:45 or 11:26). Seconds will only be reported if they were measured as part of the study.
- The last footnote will be “PROGRAM SOURCE: ...\\xx.sas, DATA CUTOFF DATE: DD Mmm YYYY, RUN DATE: DD Mmm YYYY hh:mm”.

## Missing or Incomplete Dates (i.e., Adverse Events and Concomitant Medications)

The most conservative approach will be systematically considered. If the adverse event (AE) onset date is missing/incomplete, it is assumed to have occurred during the study treatment phase (i.e., considered a treatment-emergent AE) except if the partial onset date or other data, such as the stop date, indicates differently. Similarly, a medication with partial start and stop dates could be considered as both a prior and concomitant medication.

The following algorithms will be applied to missing and incomplete start and stop dates:

### Start Dates

- If the day portion of the start date is missing, then the start date will be estimated to be equal to the date of the first dose of study drug, provided the start month and year are the same as the date of the first dose of study drug and stop date is either after the date of the first dose of study drug or completely missing. Otherwise, the missing day portion will be estimated as “01.”
- If both the day and month portions of the start date are missing, then the start date will be estimated to be equal to the date of the first dose of study drug, provided the start year is

the same as the date of the first dose of study drug and stop date is either after the date of the first dose of study drug or completely missing. Otherwise, the event will be assumed to start on the first day of the given year (e.g., ??-??-2013 is estimated as 01-JAN-2013).

- If the start date is completely missing and stop date is either after the date of the first dose of study drug or completely missing, then the start date will be estimated to be equal to the date of the first dose of study drug. Otherwise, the start date will be estimated to be the first day of the same year as the stop date. All other non-AE and nonconcomitant medication day calculations where only partial dates are available will be handled as follows: the first day of the month will be used in the calculations if the day part of a start date is missing, and January 1 will be used if both the month and day parts of a start date are missing.

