 - 7) If receiving acetylcholinesterase inhibitors (AChEI), memantine or a combination of the two, must have been on a stable dose for at least 12 weeks before the screening visit, with no plans for dose adjustment during the study. Treatment-naïve subjects can be entered into the study, but there should be no plans to initiate treatment with AChEIs or memantine from Screening to the end of the study.
 - 8) Stable pharmacological treatment of any other chronic conditions for at least 30 days prior to screening.
 - 9) Formal education of eight or more years.
 - 10) Subjects living at home or in an assisted living facility.
 - 11) Ability to swallow capsules.
 - 12) Must consent to apolipoprotein E (ApoE) genotyping.
 - 13) Subjects shall be generally healthy with mobility (ambulatory or ambulatory-aided, i.e., walker or cane), vision and hearing (hearing aid permissible) sufficient for compliance with testing procedures.
 - 14) Must be able to complete all screening evaluations.

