## 9.6 Prior and Concomitant Medications

Prior and concomitant medication verbatim terms will be mapped to the World Health Organization (WHO) Anatomical Therapeutic Chemical (ATC) classification 3 and preferred names using the WHO Drug Global dictionary (enhanced) September 2021.

Partial dates will be imputed. For details on imputation rules, refer to Appendix A: Presentation of Data and Programming Specifications. Imputed dates are only used for classification of a medication as a prior or concomitant medication; no other calculation, such as durations, will be performed using imputed dates.

- Medications that started prior to the first dose of study drug will be considered prior medications, regardless of whether or not they were stopped prior to the first dose of study drug.
- Any medications continuing or starting after the first dose of study drug will be considered concomitant medications.
- If a medication starts prior to the first dose of study drug and continues after the first dose of study drug, it will be considered both prior and concomitant.

If the medication cannot be classified as a prior or concomitant medication, the medication will be considered as concomitant.

Prior and concomitant medications will be summarized for each treatment by ATC class 3 and preferred name for the ITT population. These summaries will present the number and percentage of subjects using each medication. Subjects may have more than 1 medication per ATC class and preferred name. At each level of subject summarization, a subject is counted once if he/she reported 1 or more medications at that level. Each summary will be ordered by descending subject count in the total column by ATC level 3 and preferred name.

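### The adverse-event start-date rule in SAP Appendix A, applied to medications, can remove the prior label from drugs already in use before first dose

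*SAP*

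**What the plan says.** SAP 9.6 sends incomplete medication dates to the appendix: "For details on imputation rules, refer to Appendix A: Presentation of Data and Programming Specifications". The appendix section is titled "Missing or Incomplete Dates (i.e., Adverse Events and Concomitant Medications"), so the two kinds of record share one algorithm.

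The branch for a wholly unknown start covers drugs stopped later than Day 1 "or completely missing, then the start date will be estimated to be equal to the date of the first dose of study drug". A start date with only the year known is also set to first dose when that year is the year of first dose and the stop date is later or missing.

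SAP 9.6 then classifies on the resulting date. "Medications that started prior to the first dose of study drug will be considered prior medications", whether or not they stopped before dosing. A drug that continues past first dose is concomitant, and one that starts before and continues after is both. Imputed dates serve this classification only.

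The introduction to the appendix rules says that "a medication with partial start and stop dates could be considered as both a prior and concomitant medication".

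In the protocol, inclusion criterion 8 requires "Stable pharmacological treatment of any other chronic conditions for at least 30 days prior to screening", and section 5.2.1 lists "The change in usage of concomitant medications" as a safety endpoint.

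**The concern.** For an adverse event, moving an unknown onset to first dose is the cautious choice, because the event is then counted as treatment-emergent. For a medication the same step has a different effect: it removes the prior label from a drug that may have been taken for years. A lack of date information alone then changes the class from both to concomitant only.

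At stake is the accuracy of one descriptive summary and how it is read. The prior-medication summary loses such drugs. SAP 9.6 is also the only place where the SAP plans anything that bears on the protocol's change-in-usage endpoint, so a reader may well set the prior and concomitant summaries side by side.

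**Working it through.** The plan gives no figure to reproduce. The check applies the written rules to example records.

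**Inputs**
- Start-date rule: SAP Appendix A, Start Dates.
- Missing or continuing stop date: taken as the last known date on study (SAP Appendix A, Stop Dates).
- Prior: start date before first dose. Concomitant: continues or starts after first dose (SAP 9.6).
- First-dose date: 15 June 2023. This is an assumption for illustration; another mid-year date gives the same pattern.

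**Results**

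| Recorded start | Stop | Start used | Prior | Concomitant |
|---|---|---|---|---|
| 10 March 2015 (known) | ongoing | 10 March 2015 | yes | yes |
| wholly missing | ongoing | 15 June 2023 | no | yes |
| wholly missing | 1 Sept 2023 | 15 June 2023 | no | yes |
| 2023 only | ongoing | 15 June 2023 | no | yes |
| June 2023 | ongoing | 15 June 2023 | no | yes |
| May 2023 | ongoing | 1 May 2023 | yes | yes |
| 2015 only | ongoing | 1 Jan 2015 | yes | yes |
| wholly missing | 1 May 2023 | 1 Jan 2023 | yes | no |

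**Which rows matter for a drug already in use at screening**

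1. *Wholly missing start, ongoing or stopped after first dose.* The drug should match the first row and does not.
2. *Year of first dose only.* Criterion 8 asks for at least 30 days of stable treatment before screening, and screening ends by Day -1. A compliant chronic drug therefore started at least 30 + 1 = 31 days before Day 1, here by 15 May 2023. Any start from 1 January to 15 May 2023 fits both the criterion and a record of 2023, and the rule moves it to 15 June.
3. *Month of first dose.* Two dates in one calendar month differ by at most 30 days, which is less than 31. Such a record cannot be a compliant long-standing drug, so this row is not part of the point.
4. *Known earlier year or month, or stopped on or before first dose.* The rule classes these acceptably.

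**Does the fallback in SAP 9.6 help?** It assigns concomitant status to a drug that cannot be classified. Imputation always supplies a date, so it is not reached. If wholly missing dates were held to lie outside the imputation, the fallback would still give concomitant and not both.

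**Size per record.** Subjects count once per preferred name. With the planned 40 subjects per arm, and the arm total assumed as denominator, each affected subject lowers that drug's prior percentage by 1/40 = 2.5 points, provided the subject has no other prior record of it. The documents do not say how many subjects this will be.

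**The case against.** The best defence is that SAP 9.6 deliberately sends uncertain drugs to the concomitant side, so that nothing is lost from the on-treatment summary. That holds: every affected drug appears in the concomitant summary either way. It does not explain why the prior label should be lost as well, since 9.6 allows a drug to carry both.

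Frequency is also open. The eCRF is not among the documents and may record whether a drug was started before the study. Medications are recorded from screening, and eligibility checks should bring many dates to light. This stands, and it is why no percentage is given. The SAP rule as written uses no such field.

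Three stronger readings are tempting, and the documents do not support them.
- A reader might infer that every record meeting the rule is misclassified. Some will be drugs truly begun on study, and for those the result is right.
- A reader might infer that the change-in-usage safety endpoint acquires false starts on Day 1. The SAP defines no new-start output and does not treat concomitant-but-not-prior as a marker of one. Misreading by someone comparing the summaries is possible, but it is not a planned result.
- A reader might infer that Appendix A flatly contradicts itself. Its remark on double classification is permissive and concerns partial dates, so it does not reach wholly missing ones. The tension is limited to partial dates in the year of first dose, where the algorithm rules out an outcome that the introduction allows.

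**Conclusion.** The point holds in a narrow form. For a drug that is ongoing or stopped after first dose, with a start date wholly missing or known only to the year of first dose, the written rules give concomitant only, even when the drug was in use at screening. With a known date, SAP 9.6 would class it as both.

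The consequence is an undercount, of unknown frequency, in the descriptive prior-medication summary, and a possible misreading of those drugs as new starts. Concomitant counts are unaffected. So is the cholinesterase inhibitor/memantine subgroup, which SAP 10.6 defines by use during treatment, and so are the efficacy and adverse-event results. No imputed date enters a duration or any other calculation.

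This rests on the rules being programmed as written, without an eCRF indicator of pre-study use. The importance is low, but a stated rule gives a wrong class in a planned summary.

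**What to change.** In SAP Appendix A, limit first-dose imputation of start dates to adverse events and add a medication rule. If a missing or partial start date does not exclude a start before first dose, and the stop date is after first dose, ongoing or missing, classify the medication as both prior and concomitant. Refer to this rule in SAP 9.6.

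The cost is about two lines of text and a small programming change. The downside is that a few truly new drugs with missing or partial dates will also be counted as prior. Their concomitant counts stay the same.
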